**Monitoring for Hepatocellular Injury**

The algorithm for monitoring and interrupting study drug for treatment-emergent hepatocellular DILI signals in subjects with a normal ALT baseline value is provided in [Table 5](#).

**Table 5: Algorithm for Monitoring and Interrupting Study Drug for Treatment-Emergent Hepatocellular DILI Signals in Subjects with a Normal ALT Baseline Value**

Treatment-Emergent ALT	Bilirubin	Liver-Related Symptoms	Action
ALT $\geq 5 \times$ ULN	Normal Gilbert's syndrome or hemolysis: No change in baseline total bilirubin	None	Repeat blood tests and monitor for symptoms.
ALT $\geq 8 \times$ ULN	Normal or elevated	None or present	Interrupt study drug and repeat blood tests. Study drug can be restarted if another etiology (not hepatocellular injury) is identified and abnormalities return to baseline levels.
ALT $\geq 3 \times$ ULN	Total bilirubin $\geq 2 \times$ baseline Gilbert's syndrome or hemolysis: direct bilirubin $> 2 \times$ baseline if baseline $> 0.5$ mg/dL	None or present	
ALT $\geq 5 \times$ ULN	Normal or elevated	Present	

ALT = alanine aminotransferase; DILI = drug induced liver injury; ULN = upper limit of normal.

The algorithm for monitoring and interrupting study drug for treatment-emergent hepatocellular DILI signals in subjects with an elevated ALT baseline value is provided in [Table 6](#).

**Table 6: Algorithm for Monitoring and Interrupting Study Drug for Treatment-Emergent Hepatocellular DILI Signals in Subjects with an Elevated ALT Baseline Value**

Treatment-Emergent ALT	Bilirubin	Liver-Related Symptoms	Action
ALT $\geq 3 \times$ baseline	Normal Gilbert's syndrome or hemolysis: No change in baseline total bilirubin	None	Repeat blood tests and monitor for symptoms.
ALT $\geq 5 \times$ baseline	Normal or elevated	None or present	Interrupt study drug and repeat blood tests. Study drug can be restarted if another etiology (not hepatocellular injury) is identified and abnormalities return to baseline levels.
ALT $\geq 2 \times$ baseline	Total bilirubin $\geq 2 \times$ baseline Gilbert's syndrome or hemolysis: direct bilirubin $> 2 \times$ baseline if baseline $> 0.5$ mg/dL	None or present	
ALT $\geq 2 \times$ baseline	Normal or elevated	Present	

ALT = alanine aminotransferase; DILI = drug induced liver injury.

Monitoring for Cholestatic Injury

The algorithm for monitoring and interrupting study drug for treatment-emergent cholestatic DILI signals is provided in [Table 7](#).

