**Table 7: Algorithm for Monitoring and Interrupting Study Drug for Treatment-Emergent Cholestatic DILI Signals**

Treatment-Emergent ALP	Bilirubin	Liver-Related Symptoms	Action
ALP $\geq 2\times$ baseline without alternative explanation	Normal Gilbert's syndrome or hemolysis: No change in baseline total bilirubin	None	Repeat blood tests and monitor for symptoms.
	Total bilirubin $\geq 2\times$ baseline Gilbert's syndrome or hemolysis: direct bilirubin $> 2\times$ baseline if baseline $> 0.5$ mg/dL	None or present	Interrupt study drug and repeat blood tests. Study drug can be restarted if another etiology (not cholestatic injury) is identified and abnormalities return to baseline levels.
	Normal or elevated	Present	
ALP $\geq 3\times$ baseline without alternative explanation	Normal or elevated	None or present	

ALP = alkaline phosphatase; DILI = drug induced liver injury.

In addition to the algorithms above, the Investigator may use clinical judgement to increase monitoring for DILI or interrupt or discontinue study drug as warranted for reasons of subject safety. An episode of DILI leading to hepatic decompensation in a study subject will result in permanent study drug discontinuation.

If a subject cannot return to the study site for a scheduled or unscheduled visit, or an immediate assessment is required, the use of a local laboratory is acceptable at the discretion of the Investigator. All local laboratory values obtained as part of DILI monitoring as well as their normal ranges are to be collected and entered into the clinical database.

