Where applicable, hematology, chemistry and coagulation results for select parameters will be assigned a toxicity grade based on the U.S. Department of Health and Human Services CTCAE, version 5.0 (HHS 2017). If criteria for a grade includes a quantitative component and a clinical intervention component, the clinical intervention component will be ignored where it cannot be programmatically addressed using available data and only the quantitative portion of the criteria will be considered. If the quantitative criteria for grading are equivalent for two grades and the differentiation is described by clinical interventions, the clinical intervention component will not be considered and the highest CTCAE grade will be assigned. Similarly, death related to AE (i.e., Grade 5) cannot be determined with available laboratory-based data collection and, thus, will not be summarized as a category. Laboratory parameters that include multiple sets of criteria for each direction (e.g., separate criteria for potassium measures to assess hyperkalemia and hypokalemia) will be summarized separately to reflect each set of criteria.

Five-by-five contingency tables will be presented for lab tests where toxicity grading can be applied, to summarize the shift from the baseline grade to the worst post-baseline grade within each study treatment period and the study overall. Grades will be presented as none (Grade 0; i.e., measurements did not meet any CTCAE criteria for Grades 1 through 4), mild (Grade 1), moderate (Grade 2), severe (Grade 3), or life-threatening (Grade 4). Shift from the initiation of OLE value to the worst post-OLE value will also be provided for the Open-Label Extension Period. Summary results will include the count and percentage of subjects within each shift category, analyzed separately for each study treatment period.

The clinical study protocol includes algorithms for monitoring and interrupting study drug for treatment-emergent hepatocellular and cholestatic DILI signals based on ALT, ALP and total bilirubin values. A shift from baseline in ALT or ALP values to select treatment-emergent DILI signal criteria will be summarized for each study period and the study overall.

Subjects with post-baseline ALT values will be assessed for shift from Baseline ALT to the following DILI criteria:

Normal Baseline ALT:

- Any Instance of ALT  $\geq$  3 x ULN and Total Bilirubin  $\geq$  2 x Baseline
- Any Instance of ALT  $\geq$  5 x ULN

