- Any Instance of ALT  $\geq$  8 x ULN

Elevated Baseline ALT (ALT > ULN at Baseline):

- Any Instance of ALT  $\geq 2$  x Baseline and Total Bilirubin  $\geq 2 \times$  Baseline
- Any Instance of ALT  $\geq$  3 x Baseline
- Any Instance of ALT  $\geq$  5 x Baseline

Subjects with post-baseline ALP values will be assessed for shift from Baseline ALP to the following DILI criteria:

- Any Instance of ALP  $\geq 2$  x Baseline and Total Bilirubin  $\geq 2$  x Baseline
- Any Instance of ALP  $\geq$  3 x Baseline

Summary results will include the count and percentage of subjects within each shift category, analyzed separately for each study treatment period and the study overall.

Subjects qualifying in any of the above ALT or ALP treatment-emergent DILI criteria will be presented in a data listing to include ALT (or ALP), baseline and treatment-emergent total bilirubin, baseline and treatment-emergent direct bilirubin, Gilbert Syndrome status, and any treatment-emergent AEs reported at the time of the treatment-emergent lab date.

The clinical study protocol also includes algorithms for monitoring and interrupting study drug for treatment-emergent acute deterioration of kidney function based on laboratory parameters or clinical symptoms. Any increase in serum creatinine by  $\geq 0.3$  mg/dL from baseline and any increase in serum creatinine to  $\geq 1.5$  x baseline will be summarized for each study period and the study overall.

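### The SAP's DILI table and listing omit two symptom-based interruption situations from protocol Tables 6 and 7, and the asymptomatic ALP repeat-test level

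*SAP*

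**What the plan says.** Protocol 12.13.3 gives three algorithms. In Table 6, for subjects with elevated baseline ALT, the action for the interruption rows begins "Interrupt study drug and repeat blood tests. Study drug can be restarted if another etiology (not hepatocellular injury) is identified". One of those rows is "ALT $\geq 2 \times$ baseline" with liver-related symptoms present, whatever the bilirubin. Table 7 opens at "ALP $\geq 2\times$ baseline without alternative explanation". At that level it orders repeat tests if there are no symptoms and bilirubin is normal. If symptoms are present at any bilirubin, the action is "Interrupt study drug and repeat blood tests. Study drug can be restarted if another etiology (not cholestatic injury) is identified". The examples given of liver-related symptoms include severe fatigue, nausea and new or worsening pruritus.

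SAP 4.5.5 states: "A shift from baseline in ALT or ALP values to select treatment-emergent DILI signal criteria will be summarized for each study period". Its rows are:

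- Normal baseline ALT: ≥3× ULN with total bilirubin ≥2× baseline; ≥5× ULN; ≥8× ULN.
- Elevated baseline ALT: ≥2× baseline with total bilirubin ≥2× baseline; ≥3× baseline; ≥5× baseline.
- ALP: ≥2× baseline with total bilirubin ≥2× baseline; ≥3× baseline.

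The accompanying listing is restricted to subjects in those rows: "Subjects qualifying in any of the above ALT or ALP treatment-emergent DILI criteria will be presented in a data listing". It shows total and direct bilirubin, Gilbert's status and any TEAE at the time of the laboratory value. No row uses symptoms, and the SAP gives no reason for its selection.

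**The concern.** The DILI table and listing are the only outputs organised around the protocol's liver algorithms. If dosing can be interrupted under Table 6 or 7 and the subject still falls outside both, a reader of the study report cannot recover from them how many liver signals arose on each arm.

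The omitted triggers use the lowest multiples of baseline in Tables 6 and 7. The entry criteria admit subjects with raised enzymes, excluding only ALT or AST above 5× ULN and ALP above 10× ULN. The trigger symptoms also overlap with the complaint for which subjects are enrolled. Safety and tolerability is a secondary objective, and each arm has about 29 subjects, so a few cases would matter to how the display reads.

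**Working it through.** No figure in the plan needs reproducing. The check compares each protocol trigger with the SAP rows. TB is total bilirubin as a multiple of baseline; BL is baseline.

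| Protocol trigger | Action | Captured in SAP 4.5.5 by | Not captured |
|---|---|---|---|
| Table 5: ALT ≥5× ULN, normal bilirubin, no symptoms | repeat tests | ≥5× ULN | none |
| Table 5: ALT ≥8× ULN | interrupt | ≥8× ULN | none |
| Table 5: ALT ≥3× ULN with TB ≥2 | interrupt | same row | none* |
| Table 5: ALT ≥5× ULN with symptoms | interrupt | ≥5× ULN | none |
| Table 6: ALT ≥3× BL, normal bilirubin, no symptoms | repeat tests | ≥3× BL | none |
| Table 6: ALT ≥5× BL | interrupt | ≥5× BL | none |
| Table 6: ALT ≥2× BL with TB ≥2 | interrupt | same row | none* |
| Table 6: ALT ≥2× BL with symptoms | interrupt | only if ALT ≥3× BL or TB ≥2 | **ALT 2 to <3× BL, TB <2** |
| Table 7: ALP ≥2× BL, normal bilirubin, no symptoms | repeat tests | only if ALP ≥3× BL or TB ≥2 | **ALP 2 to <3× BL, TB <2** |
| Table 7: ALP ≥2× BL with TB ≥2 | interrupt | same row | none* |
| Table 7: ALP ≥2× BL with symptoms | interrupt | only if ALP ≥3× BL or TB ≥2 | **ALP 2 to <3× BL, TB <2** |
| Table 7: ALP ≥3× BL | interrupt | ≥3× BL | none |

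Written as rules for elevated baseline ALT, with r the ALT multiple of baseline:

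- Protocol interrupts if r ≥ 5, or (r ≥ 2 and TB ≥ 2), or (r ≥ 2 and symptoms).
- SAP captures if (r ≥ 2 and TB ≥ 2) or r ≥ 3.
- Interrupted but not captured: symptoms, 2 ≤ r < 3 and TB < 2.

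For example, r = 2.5 and TB = 1.5 with nausea meets the Table 6 symptom row, but 2.5 < 3 and 1.5 < 2, so no SAP row applies. The same algebra with ALP gives the same band in Table 7. Running the interruption rules over a grid of multiples from 1 to 10, bilirubin from 1 to 3, and symptoms present or absent confirms that, for subjects without Gilbert's syndrome or hemolysis, these two situations are the only uncovered interruptions.

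*For subjects with Gilbert's syndrome or hemolysis the bilirubin rows use direct bilirubin (above 2× baseline if baseline exceeds 0.5 mg/dL). The SAP has no such row, so with TB <2 those triggers are also missed at ALT 3 to <5× ULN (normal baseline), ALT 2 to <3× BL (elevated baseline) and ALP 2 to <3× BL.

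The omitted subjects can still appear elsewhere:

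- SAP 4.5.5 lists all laboratory data and, separately, abnormal values. It also summarises values and low/normal/high shifts by arm. A subject already high at baseline shows there as high to high.
- Protocol 12.1.4.1 makes a laboratory abnormality an AE if, among other things, it requires a study-drug adjustment or comes with symptoms outside a pre-existing diagnosis. Such an event enters the by-arm TEAE tables of SAP 4.5.3. Repeat testing of the same analyte alone does not make it an AE.
- SAP 4.5.3 lists AEs leading to discontinuation. SAP 4.5.4 mentions interruption only for SAEs and AEs of special interest, and the latter are kidney events.

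None of these marks the subject as having met a protocol DILI criterion.

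**The case against.** The strongest reply is that the SAP declares a subset and describes the algorithms as resting on ALT, ALP and total bilirubin. A table built only from laboratory values is defensible, because symptoms are hard to program. For CTCAE grades the same section drops clinical components that cannot be programmed. On ALT the SAP is consistent: it keeps every purely laboratory level of Tables 5 and 6 and drops the symptom rows. Table 5's symptom row is covered only because its threshold coincides with a repeat-test level, so that coverage is not evidence of an oversight. The table also contains repeat-test levels, and nothing says it was meant to count interruptions.

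Most of that stands, but two things remain. First, Table 7's ALP ≥2× baseline level without symptoms is a laboratory trigger, and it was dropped while the equivalent ALT repeat-test levels were kept. The laboratory-only principle does not explain that. Second, the listing already carries concurrent TEAEs, so symptom information is available there, yet entry to the listing excludes the subjects for whom it matters. For kidney function the same section tabulates both protocol creatinine thresholds, including the lower one.

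A reader might also infer that every ALT value in the 2 to <3× band is an omitted signal. It is not: Table 6 gives no action for an asymptomatic value there with bilirubin below 2× baseline.

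**Conclusion.** The point holds as a gap in safety reporting. SAP 4.5.5 leaves out two interruption situations: symptomatic ALT at 2 to <3× baseline (elevated baseline ALT) and symptomatic ALP at 2 to <3× baseline, each with total bilirubin <2× baseline. It also leaves out the asymptomatic ALP ≥2× repeat-test level. The ALP half is the stronger, because it includes a trigger that needs no symptom data.

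Three stronger readings are not supported:

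- That these subjects had dosing stopped for good. The action is interruption, with restart allowed: "Study drug can be restarted if another etiology (not hepatocellular injury) is identified and abnormalities return to baseline levels", and a parallel provision in Table 7.
- That a liver signal would vanish from the results. Only the DILI table and listing would miss it; the laboratory outputs and, where an AE is recorded, the TEAE outputs remain, without the label.
- That the effect can be sized. The documents give no proportion with elevated baseline enzymes and no expected frequency of these triggers. The figure 1/29 = 3.4% is what one subject contributes to a planned arm, not a forecast.

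Subject management follows the protocol algorithms and is unaffected, as are the efficacy analyses. This is a cheap improvement worth making before unblinding. It takes no position on which clinical threshold is right.

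**What to change.** In SAP 4.5.5:

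1. Add an ALP row for any value ≥2× baseline, regardless of bilirubin. It is slightly wider than Table 7, which requires no alternative explanation and, for asymptomatic subjects, normal bilirubin. A footnote should say so.
2. For elevated baseline ALT, add a row for ALT ≥2× baseline with a concurrent liver-related symptom TEAE, fixing the symptom terms from protocol 12.13.3 before unblinding. If symptoms cannot be programmed, use any ALT ≥2× baseline, labelled as a laboratory screen and not a protocol trigger.
3. Extend the DILI listing to these subjects, keeping the concurrent TEAEs and adding study-drug interruption where the eCRF records it.
4. State why any remaining protocol criterion is left out, including the direct-bilirubin rule for Gilbert's syndrome and hemolysis.

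The cost is two table rows and a wider listing. The laboratory values and TEAEs are already collected. The documents show no field tying an interruption to 12.13.3, so that item depends on the eCRF. The downside is that a few more subjects will be shown as meeting a criterion without liver injury. The aim is only to reconcile the SAP criteria with protocol Tables 6 and 7.

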#### 4.1.2 Definition of Baseline

Baseline will be defined as follows:

- For WI-NRS analysis, the average WI-NRS score using the daily values from the week before the first dose of study drug (Visit 2 [Day 1]) will serve as the baseline score. The WI-NRS value reported on Visit 2 [Day 1] is to be collected prior to the study visit according to the clinical study protocol and will be used in the baseline derivation. Day -6 through Day 1 will reflect the seven days of data reporting to be utilized.
- using the daily values from the 14 days before the first dose of study drug (including the WI-NRS score captured on the study day 1 of dosing) will serve as the baseline bi-weekly score.
- For all other study assessments, baseline is the last pre-treatment value available prior to the first dose of study drug.

Change from baseline summaries of the Open-Label Extension Period will utilize the same baseline definition derived in the Double-Blind Treatment Period. Change from the initiation of OLE will also be summarized for the Open-Label Extension Period summaries; change from the initiation of OLE will compare OLE assessments with the subject's Week 6 [Visit 6] reported assessment or last available measurement in the event Week 6 is not reported.

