# 4.5 Safety Evaluation

Safety analyses during the Double-Blind Treatment Period will be carried out for the Safety Analysis Set, to include all subjects who receive at least one dose of study drug. Safety analyses during the Double-Blind Treatment Period and Open-Label Extension Period will be summarized for the Open-Label Extension Analysis Set, to include all subjects who receive at least one dose of study drug during open-label participation. Safety data will be summarized separately for the Double-Blind Treatment Period and Open-Label Extension Period by randomized Double-Blind treatment received; a summary of all subjects combined within each study treatment period will also be provided. Subjects who do not complete the study, for whatever reason, will have all available data up until the time of termination included in the analysis. For safety analysis presented by study visit, the baseline value will be defined as described in Section 4.1.2 to include a Change from Baseline and Change from Initiation of OLE assessment.

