## 4.5.5 Clinical Laboratory Evaluation

All descriptive summaries of laboratory results will be based on data analyzed by the central laboratory and presented in conventional units. All data will be included in by-subject data listings. Laboratory measurements identified as abnormal (i.e., outside the normal range) will also be listed separately by subject, laboratory test, and unit. In addition, normal ranges provided by the central laboratory will be presented in a separate listing.

Clinical laboratory measurements, including serum chemistry, hematology, coagulation, and thyroid function tests, will be summarized by treatment group and all subjects combined for each study treatment period. Descriptive statistics will be presented for observed values and changes from baseline at each visit where parameters

were scheduled to be collected per the clinical study protocol. A summary by safety subgroups of interest (type of cholestatic disease and baseline eGFR) described in Section 4.4.7.8 will be provided for the univariate summaries of chemistry and hematology using the Safety Analysis Set and Open-Label Extension Analysis Set. Change from the initiation of OLE will also be presented in the Open-Label Extension Period summaries.

Where applicable, laboratory results will be classified as "low," "normal," or "high" with respect to the parameter-specific reference ranges (i.e., below the lower limit of the normal range, within the normal range, or above the upper limit of the normal range). Three-by-three contingency tables will be presented for each laboratory parameter to summarize the shift from the baseline category to the worst post-baseline measurement within each treatment period, defined as the value numerically farthest outside of the normal range across all post-baseline visits through the end of each study treatment period and the study overall. Shift from the initiation of OLE value to the worst post-OLE value will also be provided for the Open-Label Extension Period. Summary results will include the count and percentage of subjects within each shift category and treatment group separately for each study treatment period and the study overall.

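### The SAP's open-label DILI-criteria and creatinine threshold tables have no Week 6 reference, so they can misclassify placebo subjects who first receive EP547 in that period

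*SAP*

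**What the plan says.** SAP 4.1.2 sets the reference for laboratory data: "baseline is the last pre-treatment value available prior to the first dose of study drug". Study drug includes placebo (SAP 3.1). For the open-label period the same section adds that "Change from baseline summaries of the Open-Label Extension Period will utilize the same baseline definition derived in the Double-Blind Treatment Period", followed by a general statement: "Change from the initiation of OLE will also be summarized for the Open-Label Extension Period summaries". SAP 4.5 then applies the two references in narrower terms: "For safety analysis presented by study visit, the baseline value will be defined as described in Section 4.1.2", with change from baseline and change from OLE initiation both named.

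SAP 4.5.5 goes through the laboratory outputs one at a time. Change from OLE initiation is written out for the by-visit summaries. For the low/normal/high shift tables, and again for the CTCAE grade shift tables, it says: "Shift from the initiation of OLE value to the worst post-OLE value will also be provided for the Open-Label Extension Period".

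The last two outputs in 4.5.5 are built on the protocol's liver and kidney monitoring criteria. For the liver: "A shift from baseline in ALT or ALP values to select treatment-emergent DILI signal criteria will be summarized for each study period". For the kidney, it counts any creatinine increase of at least 0.3 mg/dL from baseline and any increase to at least 1.5 x "baseline will be summarized for each study period and the study overall". Neither has an OLE-initiation version.

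**The concern.** Subjects randomized to placebo who complete six weeks and are still on study drug take their first EP547 dose at the start of the open-label period. For them the pre-EP547 laboratory value is the Week 6 sample, which the protocol (9.4.2.5) has drawn before the open-label dose. Day 1 is the value before placebo.

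Safety data in the open-label period are shown by randomized arm (SAP 4.5), so former-placebo subjects have their own column. A reader will take that column as what happened after first exposure to EP547. With Day 1 as the only reference, it mixes six weeks of placebo-period movement with the change on drug. Kidney and liver are the two organs for which the protocol writes specific monitoring criteria. The group is small and has two scheduled on-EP547 laboratory visits after starting, Days 64 and 85 (Protocol Appendix A). A single misclassified subject would therefore be visible. For subjects randomized to EP547 the issue does not arise, because Day 1 is their pre-EP547 value.

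**Working it through.** **1. Outputs in SAP 4.5.5, side by side**

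| Output | Day 1 baseline | OLE-initiation version |
|---|---|---|
| By-visit values and changes | yes | yes |
| Low/normal/high shift to worst value | yes | yes |
| CTCAE grade shift to worst grade | yes | yes |
| DILI-criteria table | yes | not stated |
| Creatinine threshold summary | yes | not stated |

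The last two count any instance within a period. They are not presented by visit, so the two-reference rule in SAP 4.5 does not plainly reach them.

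**2. How far the criteria depend on Day 1.** There are 10 criteria: 3 for normal baseline ALT, 3 for elevated baseline ALT, 2 for ALP and 2 for creatinine. Eight contain a multiple of baseline or a difference from it. The other two (ALT at least 5x and at least 8x ULN) have fixed cut-offs, but Day 1 ALT still decides whether a subject is assessed under them.

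**3. Hypothetical former-placebo subjects, with the SAP's own cut-offs.** Creatinine is in mg/dL; ALP and ALT are in U/L. The ALT rows assume a ULN below 60 (ALT elevated at every visit).

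| Test | Day 1 / Week 6 / OLE | Against Day 1 | Against Week 6 |
|---|---|---|---|
| Creatinine | 0.8 / 1.1 / 1.1 | 1.1 − 0.8 = +0.3; 1.1/0.8 = 1.38x: flagged (≥0.3) | 0.0; 1.0x: not flagged |
| Creatinine | 1.0 / 0.8 / 1.2 | +0.2; 1.2x: not flagged | 1.2 − 0.8 = +0.4; 1.2/0.8 = 1.5x: both flags |
| ALP | 200 / 600 / 600 | 3.0x: flagged (≥3x) | 1.0x: not flagged |
| ALP | 300 / 190 / 600 | 2.0x: ≥3x not met | 600/190 = 3.2x: flagged |
| ALT | 60 / 180 / 180 | 3.0x: flagged (≥3x) | 1.0x: not flagged |
| ALT | 100 / 60 / 190 | 1.9x: not flagged | 190/60 = 3.2x: flagged |

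Day 1 can also put a subject in the wrong ALT set. Take ALT at 2.5x ULN on Day 1, 0.9x ULN at Week 6 and 5x ULN on EP547, with no doubling of bilirubin. Against Day 1 the ratio is 5/2.5 = 2.0, below the 3x cut-off, so there is no flag. With Week 6 as reference, ALT is normal at the start and the 5x ULN criterion is met. Elevated Day 1 ALT is possible, since only values above 5x ULN are excluded at entry.

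**4. When the reference matters.** This is an illustrative simulation of the 0.3 mg/dL criterion. Assumptions, none from the documents: true level 0.85 mg/dL; within-subject SD 0.05 to 0.12; placebo-period change p; EP547 change d; two open-label visits. A subject is flagged if the larger open-label value minus the reference is at least 0.3.

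| p | d | Flagged against Day 1 | Flagged against Week 6 |
|---|---|---|---|
| +0.2 | 0 | 13.5% to 41.6% | 0.0% to 6.8% |
| −0.1 | +0.3 | 13.4% to 41.5% | about 67% |
| 0 | +0.3 | about 67% | about 67% |
| 0 | 0 | 0.0% to 6.9% | 0.0% to 6.8% |

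With no movement on placebo the two references perform alike. The discrepancy comes entirely from movement between Day 1 and Week 6.

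**5. Size of the group.** The plan's own figure reproduces: 26/(1 − 0.10) = 28.9, so 29 per arm. Of 29 placebo subjects, about 26 are expected to complete. One misclassified subject is 1/29 = 3.4 or 1/26 = 3.8 percentage points.

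**The case against.** **The general sentence in SAP 4.1.2 may already cover these tables.** It says that change from OLE initiation will be summarized for the open-label period, and a creatinine increase is a change. That is a fair reading. But SAP 4.5 ties the two references to analyses by visit, and 4.5.5 restates the OLE version output by output and leaves it out here. A programmer could reasonably produce Day 1 only, so the text needs settling either way.

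**The tables mirror the protocol's monitoring criteria.** Protocol 12.13.4 points to the value before starting study drug, and the DILI algorithms in 12.13.3 use multiples of baseline. Counting subjects against those criteria is a legitimate purpose. This stands, and it is why the Day 1 version should stay.

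**Other planned outputs show much of the signal.** By-visit change from OLE initiation is split by arm and reports the maximum, so the 1.0/0.8/1.2 subject puts the former-placebo maximum at Week 9 or later at +0.4 or more. The 0.8/1.1/1.1 subject already meets the criterion in the double-blind table. All results are listed. This stands too. It does not supply the threshold count, and the DILI listing contains only subjects who qualify under the stated criteria, so a missed subject is absent from it.

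**A stronger reading is tempting:** that the conclusions on kidney adverse events of special interest are wrong for crossovers. The documents do not support it. Those events are reported adverse events summarized as TEAEs (SAP 3.4.3.1 and 4.5.3), and TEAE emergence in the open-label period is anchored to the Week 6 dose. Nor are the tables wrong for every placebo subject: those stable to Week 6 are classified the same way by either reference.

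**Conclusion.** The point holds as a limited one. As written, the open-label DILI-criteria table and creatinine threshold summary refer to the value before study drug, and no text clearly adds the OLE-initiation reference that neighbouring laboratory outputs have. For former-placebo subjects the counts can err in either direction, but only when the value moved enough between Day 1 and Week 6 to cross a cut-off.

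The group is at most 29 subjects, about 26 if the assumed 10% withdrawal rate holds. The number actually misclassified cannot be estimated from the documents, which give no within-subject variability; the simulated percentages only show how the error behaves under stated assumptions. The effect is confined to these two descriptive tables and the DILI listing. It does not reach the analysis of adverse events of special interest, the other laboratory summaries or any efficacy result. It is still worth correcting before the tables are programmed, because these are the outputs a reader will consult for kidney and liver threshold crossings on first exposure to EP547.

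**What to change.** In SAP 4.5.5, for the Open-Label Extension Period, also present the DILI-criteria table with its listing, and the creatinine threshold summary, using the OLE-initiation value as reference (Week 6 pre-dose or, if missing, the last value before open-label dosing), by randomized arm. State that this version is used to describe changes after first EP547 exposure in former-placebo subjects. For the ALT criteria, say that the normal or elevated category is reassigned from the same OLE-initiation value.

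Keep the Day 1 version, labelled as the summary of the protocol's monitoring criteria. No clinical monitoring rule changes.

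The cost is one more version of two descriptive tables and one listing. The data are already collected, and the OLE-initiation value is already needed for the other laboratory outputs.
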